6.5.5.2. EQ-5D-5L Analyses

The 5-dimension single-item 5-level EQ-5D-5L responses will be summarized using frequency distributions for each dimension and for each assessment time by treatment arm.

The index score and the VAS will be presented using summary statistics for continuous variables for each assessment time by treatment arm.

6.5.6. Analyses of Safety Data

The 'safety population' as defined in the Section 6.3.2 will be used in the analysis of safety.

In addition, selected AE summaries will be provided for subgroups including age, gender, and race; additional subgroups may be evaluated.

6.5.6.1. Study Drug Exposure

The following exposure-related variables will be reported using summary statistics (number of patients, mean, and standard deviation) by treatment group:

- Exposure: duration of treatment; number of cycles received; number of patients completing ≥ 1 cycle, ≥ 2 cycles, ..., ≥ 6 cycles, and mean, standard deviation; number of patients with dose adjustments: dose reduction, dose delay, and dose omission;
- Reasons for dose adjustments.

The following exposure-related variables will be reported using summary statistics (number of patients, mean, standard deviation, median, first and third quartiles, minimum, and maximum) by treatment group:

- Dose intensity: cumulative dose; weekly dose intensity; relative dose intensity, overall weekly dose intensity, overall relative dose intensity.

Details of study drug administration will be included in patient listings.

The number and percentage of patients having received any premedication will be presented by Anatomical Therapeutic Chemical level 2. Selected combinations of premedication will also be summarized.

6.5.6.2. Overall Summary of Adverse Events

All adverse events (AEs) will be summarized by MedDRA System Organ Class (SOC) and PT. The incidence and percentage of patients with at least one occurrence of a preferred term will be

included, according to the most severe National Cancer Institute - Common Terminology Criteria for Adverse Events (NCI-CTCAE) Version 4.0 grade.

An overall summary of AEs will be provided to summarize the following categories using frequency counts and percentages:

- patients with at least 1 TEAE, SAE, Common Terminology Criteria for Adverse Events (CTCAE) Grade ≥ 3 TEAE
- patients with AEs that led to death
- patients with AEs that led to study treatment discontinuation
- patients with SAEs that led to study treatment discontinuation.

The summary will be provided for regardless of study drug causality, and repeated for events deemed by the investigator to be related to study treatment.

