8.1. Summary of Study Design

Study JVDE is a global, multicenter, randomized, double-blind, placebo-controlled Phase 3 study evaluating the efficacy and safety of ramucirumab as a single agent for the treatment of patients with advanced HCC and elevated baseline AFP after intolerance or progression on prior sorafenib therapy. The primary objective is to compare the overall survival of HCC patients treated with ramucirumab versus patients treated with placebo. Patients with a baseline AFP ≥ 400 ng/mL, based on local laboratory results, who meet all other inclusion/ exclusion criteria, will be enrolled. The study will randomize (in a 2:1 ratio) approximately 279 patients with a baseline AFP ≥ 400 ng/mL to receive ramucirumab 8 mg/kg or placebo administered intravenously once every 14 days in an outpatient setting. All patients will be offered best supportive care (BSC), as determined appropriate by the investigator. Study treatment will continue until disease progression, unacceptable toxicity, withdrawal of consent, or until other withdrawal criterion is met.

Figure JVDE.1 illustrates the study design.

Abbreviations: D = Day; ECOG PS = Eastern Cooperative Oncology Group performance status; HCC = hepatocellular carcinoma; iv = intravenous; N = number of randomized patients; q = every; vs = versus.

^a Stratified by region (Region 1 vs Region 2 vs Region 3), macrovascular invasion (yes vs no), and ECOG PS (0 vs 1). Region 1 includes the Americas, Europe, Israel, and Australia; Region 2 includes Asian countries (excluding Japan); and Region 3 includes Japan only.

Figure JVDE.1. Illustration of study design.

The following terms describe the stages through which the patients will progress during the course of the study, as shown in Figure JVDE.2. Refer to the study schedule (Attachment 1) for the timing of procedures to be performed at each stage of the study.

- **Baseline:** begins when the ICF is signed and ends at the first study treatment (or at discontinuation, if no treatment is given). All assessments required for eligibility must be performed prior to randomization.
- **Study Treatment Period:** begins at the first study treatment and ends when the patient and the investigator agree that the patient will no longer continue study treatment. The date of this agreement is to be reported on the case report form (CRF) as the *Date of Discontinuation* from study treatment.

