10.3.1.1.11. Liver Failure and Other Significant Liver Injury

Liver failure or other significant liver injury events, such as hepatic encephalopathy, have been observed in patients with advanced HCC receiving ramucirumab.

In REACH, the incidence of any-grade liver failure / liver injury events, including clinical and laboratory events, was higher in the ramucirumab arm (50.5%) compared with the placebo arm (37.3%). Any-grade clinical events reported at a higher rate in the ramucirumab arm included hepatic encephalopathy and ascites. There was no difference in the incidence of Grade 3/4 liver failure/injury in the ramucirumab arm (19.1%) compared with the placebo arm (22.5%). No Grade 5 events of hepatic encephalopathy or ascites were observed.

Discontinue study treatment if the patient experiences hepatic encephalopathy and/or hepatorenal syndrome ([Table JVDE.3](#)).

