12.2.11. Safety Analyses

All safety summaries and analyses will be based on the safety population as defined in Section 12.2.1, unless otherwise indicated, and include:

- Adverse events will be summarized by MedDRA System Organ Class and Preferred Term (PT), classified from verbatim terms. The incidence and percentage of patients with at least 1 occurrence of a PT will be included, according to the most severe CTCAE grade. Causality (relationship to study drug), action taken, and outcome will be summarized separately. Duration of AEs will be determined and included in the listings.
- Study drug exposure will be summarized for each arm with following variables: number of infusion, number of cycles, duration of therapy, cumulative dose, dose intensity, and relative dose intensity.

- Laboratory results will be classified according to the NCI-CTCAE, Version 4.0. Incidence of laboratory abnormalities will be summarized.
- Hospitalizations due to AEs, transfusions, and vital signs will be summarized.

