6.2.2. Determination of Sample Size

The primary objective of this study is to compare ramucirumab versus placebo in terms of OS in patients with advanced HCC after intolerance or progression on prior sorafenib. The sample size was determined based on the following assumptions:

- hazard ratio (treatment/control) of 0.67, with median OS of 4.5 months in the placebo arm and 6.7 months in the ramucirumab arm
- the randomization ratio is 2:1 (ramucirumab:placebo)
- the overall significance level will be controlled at 1-sided 0.025 (2-sided 0.05)
- the Type II error rate is 20%; that is, the statistical power of the trial is set to 80%

Under the assumptions above, the final analysis will be performed when at least 221 deaths have been observed. Therefore, the study will randomize approximately 279 patients (that is, 20% censoring rate including dropouts, with approximately 186 patients randomized to the ramucirumab arm and 93 patients randomized to the placebo arm).

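### Adverse events are tabulated only as crude patient percentages although time at risk may differ by arm; exposure-adjusted rates should be added for events that accumulate over time.

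*SAP*

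**What the plan says.** The safety profile is a secondary objective in both documents (Protocol 6.2, SAP 5.2).

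- **Measure.** SAP 6.5.6.2 plans "The incidence and percentage of patients with at least one occurrence of a preferred term", by worst grade, and an overall summary of counts and percentages. Protocol 12.2.11 agrees: "The incidence and percentage of patients with at least 1 occurrence of a PT will be included, according to the most severe CTCAE grade". Under SAP 6.5.6.3 a patient counts once per term. SAP 6.5.6.4 lists SAE and AESI summaries and names no measure for AESIs.
- **Treatment length.** Protocol 8.1: "Study treatment will continue until disease progression, unacceptable toxicity, withdrawal of consent, or until other withdrawal criterion is met". Protocol 7.3.2 lets treatment go on past radiographic progression when the investigator sees benefit, and lists toxicity among the reasons to stop.
- **Collection window.** Protocol Table JVDE.6 and SAP 6.2 collect all AEs through treatment and about 30 days of short-term follow-up. In long-term follow-up only related SAEs are collected.
- **Exposure.** SAP 6.5.6.1 summarizes duration of treatment and cycles by arm, separately from the AE tables. SAP Appendix 2 adds numbers of events and of patients at risk by preferred term; the latter is a headcount, not person-time.
- **Earlier trial.** Protocol Section 5 reports a robust PFS improvement in REACH. Protocol 10.3.1.1.11 says any-grade liver failure/injury "was higher in the ramucirumab arm (50.5%) compared with the placebo arm (37.3%)". Protocol 10.3.1.1.5 gives any-grade bleeding of 32.5% versus 19.9%. The same two sections report no difference for the severe events: Grade 3 or higher bleeding 6.1% versus 7.6%, and Grade 3/4 liver events 19.1% versus 22.5%.

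**The concern.** A crude percentage estimates the chance of at least one event over whatever time each patient was observed. It compares arms fairly only when observation time is similar. Here that time is treatment time plus a common tail, and treatment time depends partly on the efficacy result. If JVDE shows a PFS benefit, the ramucirumab arm will probably be watched longer and will record more of any event that also occurs without the drug. Such events are common in this population: the REACH placebo arm had 37.3% any-grade liver failure/injury and 19.9% any-grade bleeding.

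At stake is how the liver and bleeding tables are read. No between-arm test of AEs is planned, but percentages set side by side will be compared, as the protocol itself does for REACH. Part of an excess could be observation time, and a result that looks even could be a lower rate on ramucirumab.

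**Working it through.** **1. The plan's own calculation.** The only design figure that can be recomputed concerns overall survival. SAP 6.2.2 assumes a hazard ratio of 0.67 (medians of 6.7 and 4.5 months), 2:1 allocation, a two-sided level of 0.05 and 80% power. The Schoenfeld formula gives (1.960 + 0.842)² / [(2/3)(1/3)(ln 0.67)²] = 220.2, so 221 deaths, as stated. Then 221/0.80 = 276.25, or 277 patients against 279 planned. The figure reproduces, and this point does not affect it.

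**2. Inputs for the safety illustration.** The percentages are the REACH figures above. The ratio r of time at risk (ramucirumab/placebo) is in neither document and is assumed. Illustrative treatment times, each plus 4 weeks of follow-up, give:
- equal durations: r = 1.0
- 10 versus 8 weeks: 14/12 = 1.17
- 12 versus 8 weeks: 16/12 = 1.33
- 12 versus 6 weeks: 16/10 = 1.60

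**3. Equal hazards, unequal time.** Let p be the placebo percentage, and let the constant hazard be the same in both arms.
- Fixed time at risk: 1 − (1 − p)^r
- Exponential time at risk: rh/(1 + rh), with h = p/(1 − p)

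For example, at r = 1.33 the liver figure is 1 − 0.627^1.333 = 46.3% (fixed), or with h = 0.373/0.627 = 0.595, 0.793/1.793 = 44.2% (exponential).

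| r | Liver, from 37.3% (exponential / fixed) | Bleeding, from 19.9% (exponential / fixed) |
|---|---|---|
| 1.0 | 37.3 / 37.3 | 19.9 / 19.9 |
| 1.17 | 41.0 / 42.0 | 22.5 / 22.8 |
| 1.33 | 44.2 / 46.3 | 24.9 / 25.6 |
| 1.60 | 48.8 / 52.6 | 28.4 / 29.9 |

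At r = 1.33, observation time alone would supply about 7 (exponential) to 9 (fixed) of the 13.2-point REACH liver gap, and 5.0 to 5.7 of the 12.6-point bleeding gap.

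**4. Ratio needed to explain the whole any-grade excess.**
- Liver: ln(0.495)/ln(0.627) = 1.51 (fixed); (0.505/0.495)/(0.373/0.627) = 1.71 (exponential)
- Bleeding: ln(0.675)/ln(0.801) = 1.77 (fixed); (0.325/0.675)/(0.199/0.801) = 1.94 (exponential)

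**5. The severe events.** At r = 1 the implied rate ratios (ramucirumab/placebo) are 0.79-0.80 for Grade 3 or higher bleeding and 0.81-0.83 for Grade 3/4 liver events. Dividing by 1.33 gives 0.59-0.60 and 0.61-0.62. Longer ramucirumab observation would therefore make these contrasts more favourable to ramucirumab.

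**6. The common tail dilutes the imbalance.** With mean placebo treatment of m months, a treatment-time ratio R and about 1 month of follow-up, r = (mR + 1)/(m + 1). For m from 1.5 to 4 (assumed), R = 1.49 becomes 1.29-1.39, and R = 2.0 becomes 1.60-1.80. The value 1.49 is the planned median OS ratio, 6.7/4.5, used only as a marker.

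**The case against.** The strongest reply is that unequal time at risk is inferred. Neither document gives treatment duration or PFS times by arm for either trial. Treatment may outlast radiographic progression, and stopping for toxicity could shorten ramucirumab exposure. This stands: r = 1.0 is possible, and the direction is an expectation.

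Second, the plan already holds relevant material. Mean treatment duration by arm and the Appendix 2 event counts would allow an approximate event rate per treatment week. Deaths are split by time window, AE dates are listed, and the IDMC sees unblinded safety data. It would therefore be too strong to say that the plan leaves readers no means of separating drug effect from observation time. But these items reveal an imbalance and are not linked to the percentages: no planned output adjusts for it.

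Third, safety reporting here is descriptive and crude tables are usual. That stands, and the crude tables should stay.

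A reader might infer that the crude tables could conceal ramucirumab toxicity. On the expected premise of longer ramucirumab observation they cannot: the percentages lean toward apparent harm, and what they can hide is a lower ramucirumab rate. Hidden harm would require shorter ramucirumab observation, which the documents do not predict. A reader might also infer that the REACH liver excess was only an exposure effect. The documents do not show this, since the ratio needed is model-dependent and the actual ratio is not given.

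**Conclusion.** The point holds as a worthwhile, inexpensive improvement to the safety analysis. AE tables that ignore time at risk can mislead in this design, in a direction set by which arm is observed longer. Across the assumed ratios of 1.0 to 1.60, equal hazards would add 0 to about 15 points to a 37.3% liver-injury percentage and 0 to about 10 points to a 19.9% bleeding percentage.

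These sizes rest on an assumed ratio, a hazard that is constant and equal in the two arms, and one of two simple models for time at risk. They show sensitivity and do not estimate bias in JVDE. The primary analysis, sample size and type I error control are unaffected.

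**What to change.** Keep the crude tables and add the following to SAP 6.5.6.4, before unblinding so that the adjustment is not chosen after an imbalance is seen.

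1. For Grade 3 or higher TEAEs, SAEs and the AESIs that accumulate over time (at least liver failure/injury and bleeding), report total time at risk by arm. Count it from first dose to the earliest of first event, end of the 30-day follow-up, death or data cutoff. Report patients with a first event per 100 patient-years, with the rate difference and 95% CI.
2. For liver failure/injury and bleeding, add cumulative incidence of the first event by arm, with death as a competing event.
3. Do not use constant-hazard rates for events clustered early, such as infusion-related reactions.

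The cost is a few tables and two figures from dates already collected. The rates assume a roughly constant hazard, which the curves let readers check for liver failure/injury and bleeding only. Neither measure corrects for patients whose treatment, and hence AE collection, ended because their health was declining; the text should say so.

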6.5.6.3. Treatment-Emergent Adverse Events

Causality (relationship to study drug) as determined by the investigator will be separately summarized. Missing classifications concerning study medication relationship will be considered as related to study medication. Start and end dates of AE will be included in the listings along with action taken, and outcome. If more than one AE is recorded for a patient within any SOC or PT term, the patient will only be counted once on the most severe grade and the closest relationship to treatment.

The following set of summaries will be provided for any TEAE:

- By SOC and PT (all grade and Grade ≥ 3)
- By PT (all grade and Grade ≥ 3) by decreasing frequency on ramucirumab arm
- By consolidated terms
- By maximum Grade 1-5

These summaries will also be produced for TEAEs considered related, by the investigator, to study treatment.

All collected AEs (treatment emergent or non-treatment emergent) will be presented in a listing.

6.5.6.4. Deaths, SAEs, and Other Significant Adverse Events

Reasons for deaths (study disease, AE [any AE, study treatment-related AE]) will be summarized separately for 1) all deaths, 2) death on treatment, 3) death within 30 days of study treatment discontinuation, and 4) deaths after 30 days of study treatment discontinuation.

Serious adverse events will be summarized by SOC and PT, by PT, and repeated for events deemed by the investigator to be possibly related to study medication, with consolidated summary performed if needed. A listing of SAEs will be produced.

In addition, the following analyses will be performed (*repeated for events deemed by the investigator to be possibly related to study medication, †include consolidated summary):

- Adverse events leading to death by PT†
- Adverse events leading to study treatment discontinuations by PT†
- Adverse events leading to study treatment dose modification by PT†
- Adverse events of Special Interests

Listing of AESI will be provided.

6.5.6.5. Vital Signs and Other Observations Related to Safety

For systolic and diastolic blood pressure, shift from baseline to pre and post ramucirumab/placebo administration will be summarized at each assessment time point using summary statistics according to the following categories:

- Systolic blood pressure (<140, 140-<160, ≥160 mmHg)
- Diastolic blood pressure (<90, 90-<100, ≥100 mmHg)

Weight at baseline will be presented using summary statistics. Changes from baseline to on-treatment weight assessments will be presented by time point by considering the frequency of patients with changes falling in the following categories: <-10% (loss), ≥-10% - <10%, ≥10% (gain).

A summary of ECOG PS at each scheduled time point will be provided. Refer to Section [6.5.3.3.3](#) for analysis of ECOG PS.

Listings of ECOG and vital signs will be provided.

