- [27] The patient is currently enrolled in a clinical trial involving an investigational product or nonapproved use of a drug or device or is concurrently enrolled in any other type of medical research judged not to be scientifically or medically compatible with this study. Patients participating in surveys or observational studies are eligible to participate in this study.
- [28] The patient discontinued from study treatment from another clinical trial within 28 days prior to randomization.
- [29] The patient has a known allergy or hypersensitivity reaction to any of the treatment components.
- [30] The patient has uncontrolled hypertension, as defined in CTCAE Version 4.0, prior to initiating study treatment, despite antihypertensive intervention.

CTCAE Version 4.0 defines uncontrolled hypertension as Grade >2 hypertension; clinically, the patient continues to experience elevated blood pressure (systolic >160 mm Hg and/or diastolic >100 mm Hg) despite medications).

- [31] The patient experienced any arterial thrombotic event, including myocardial infarction, unstable angina, cerebrovascular accident, or transient ischemic attack, within 6 months prior to randomization.
- [32] The patient experienced any bleeding episode considered life-threatening, or any Grade 3 or 4 gastrointestinal/variceal bleeding episode in the 3 months prior to randomization requiring transfusion or endoscopic or operative intervention.

- [33] The patient has esophageal or gastric varices that require immediate intervention (for example, banding or sclerotherapy) or represent a high bleeding risk in the opinion of the investigator or consulting gastroenterologist or hepatologist. Patients with evidence of portal hypertension (including splenomegaly detected radiographically) or any prior history of variceal bleeding must have had endoscopic evaluation within the 3 months immediately prior to randomization.
- [34] The patient has a history of gastrointestinal perforation and/or fistulae within 6 months prior to randomization.
- [35] The patient has symptomatic congestive heart failure (New York Heart Association II-IV), unstable angina pectoris, or symptomatic or poorly controlled cardiac arrhythmia.
- [36] The patient is pregnant or breast-feeding.

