Study treatment may be delayed for up to 21 days to allow time for a patient to recover from an AE or laboratory toxicity. If a patient misses ≥ 2 consecutive doses or requires a dose delay of > 21 days, continuation of study treatment may be considered after consultation with the Lilly CRP, if both of the following criteria are met:

- the events related to the missed/delayed doses have been resolved
- the patient shows evidence of ongoing disease control

Table JVDE.3. Dose-Modification Guidelines for Adverse Events of Special Interest

Adverse Event of Special Interest		Dose Modification
1.	Infusion-related reaction (Section 10.3.1.1.1)	
1.a.	
 Infusion-related reaction - Grade 1 or 2 	
Reduce the infusion rate by 50% for the duration of the infusion and for all future infusions.
 
Prior to all future infusions, premedicate with:
 
 a histamine H1 antagonist, such as diphenhydramine hydrochloride dexamethasone or equivalent acetaminophen
1.b.	
 Infusion-related reaction - Grade 3 or 4 	Discontinue study treatment.
2.	Hypertension (Section 10.3.1.1.2)	
2.a.	
 Hypertension (non-life-threatening) - Grade 2 or 3 	
Delay ramucirumab until the hypertension is controlled with medication and is resolved to Grade <2.
 
 If controlled with medication and resolved to Grade <2, then resume study treatment at current dose. If not controlled with medication and not resolved to Grade <2 within 21 days, then discontinue study treatment. For patients with asymptomatic Grade 2 hypertension, investigators have the discretion to consider the clinical circumstances of individual patients and administer unchanged dose of study treatment.
2.b.	
 Uncontrolled hypertension, hypertensive crisis, or hypertensive encephalopathy - Grade 4 	Discontinue study treatment.
3.	Proteinuria (Section 10.3.1.1.3)	

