10.3.1.1.2. Hypertension

An increased incidence of severe hypertension (CTCAE Grade 3) has been reported in patients receiving ramucirumab. In most cases, hypertension was controlled using standard antihypertensive treatment. In REACH, no Grade 4 or Grade 5 hypertension events were observed.

Monitoring of blood pressure is required during ramucirumab therapy. Every attempt should be made to control blood pressure to systolic blood pressure (BP) <140 mm Hg and diastolic BP <90 mm Hg prior to starting treatment with ramucirumab/placebo.

Dose-modification guidelines for patients experiencing hypertension are provided in [Table JVDE.3](#).

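### The SAP's only summary of measured blood pressure is tied to infusions that the protocol withholds for hypertension, and has no worst-on-study shift, so it may understate high readings

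*SAP*

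**What the plan says.** SAP 6.5.6.5 plans a "shift from baseline to pre and post ramucirumab/placebo administration will be summarized at each assessment time point". The systolic categories are "Systolic blood pressure (<140, 140-<160, ≥160 mmHg"), and the top diastolic category starts at 100 mmHg. The same section plans a listing of vital signs. No other summary of measured blood pressure is stated.

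For non-life-threatening Grade 2 or 3 hypertension, Protocol 9.4.2, Table JVDE.3, line 2.a, reads "Delay ramucirumab until the hypertension is controlled with medication and is resolved to Grade <2". It adds: "If not controlled with medication and not resolved to Grade <2 within 21 days, then discontinue study treatment". For asymptomatic Grade 2, "investigators have the discretion to consider the clinical circumstances of individual patients and administer unchanged dose of study treatment". Line 2.b stops treatment for Grade 4.

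Protocol Attachment 1 schedules vital signs at baseline, every cycle and Day 30 of short-term follow-up. Its vital-signs footnote ties the on-treatment readings to the infusion. Under Protocol 9.4.2 a missed dose uses up no cycle number, because the next dose given takes the number after the last dosed cycle.

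Protocol 10.3.1.1.2 states: "An increased incidence of severe hypertension (CTCAE Grade 3) has been reported in patients receiving ramucirumab". For graded laboratory values, SAP 6.5.6.5.1 already plans a baseline-to-worst shift, graded on the numbers alone.

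**The concern.** Whether an infusion is given depends partly on blood pressure, and the table is organised by infusion. A table restricted to readings around infusions that took place would be selected on the quantity it summarises. The withholding rule applies in both arms. If ramucirumab raises blood pressure more often, more of its high readings are exposed to removal, and the difference between arms in the table shrinks.

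The layout is a separate limitation. Shifts by time point show how many patients were in a category at each visit. They do not show how many were ever in it, which is the usual question for a known effect of this kind.

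At stake is a descriptive safety table for a listed adverse event of special interest. No hypothesis test, alpha, power or efficacy result is involved.

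**Working it through.** The plan states no figure here to reproduce. The check is a comparison of texts, followed by an illustration on assumed values.

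**Texts side by side**

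1. Entry to the table (SAP 6.5.6.5) is described by reference to administration.
2. Administration is delayed or stopped for Grade 2 to 4 hypertension (Table JVDE.3, lines 2.a and 2.b), with discretion only for asymptomatic Grade 2.
3. The visit at which a dose is withheld has no cycle number of its own (Protocol 9.4.2). The pre-infusion reading for the next dosed cycle may be the later, controlled one.
4. Day 30 readings have no administration to precede or follow.
5. The SAP neither includes nor excludes the readings in steps 3 and 4, nor unscheduled ones.

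**Illustration (every input is an assumption)**

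Assume patient mean systolic 128 mmHg (SD 10), visit-to-visit SD 10, and a ramucirumab effect e of 5, 10 or 15 mmHg. Pre-infusion readings then have SD √(10² + 10²) = 14.14, and P(reading ≥160) = 1 − Φ((160 − 128 − e)/14.14):

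- placebo, e = 0: 32/14.14 = 2.26, giving 1.2%
- e = 5: 27/14.14 = 1.91, giving 2.8%
- e = 10: 22/14.14 = 1.56, giving 6.0%
- e = 15: 17/14.14 = 1.20, giving 11.5%

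Let p be this probability and h the share of visits at ≥160 where the infusion is withheld. Suppose that lower readings are all dosed and only dosed visits are counted. The table then shows p(1 − h)/(1 − ph). At e = 10:

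- h = 0: 6.0% versus 1.2%, a difference of 4.8 points
- h = 0.5: 3.0/97.0 = 3.1% versus 0.6/99.4 = 0.6%, a difference of 2.5 points
- h = 1: 0% versus 0%, no difference

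A simulation on the same inputs took h = 1 and varied the share of 140-<160 visits that are dosed. The post-infusion reading keeps half of the pre-infusion deviation from the patient's mean, plus noise of SD 9. At e = 10, ramucirumab / placebo, in per cent:

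| Reading | All scheduled visits | Dosed visits, 0% of 140-<160 dosed | 50% dosed | 100% dosed |
|---|---|---|---|---|
| Pre ≥160 | 6.0 / 1.2 | 0 / 0 | 0 / 0 | 0 / 0 |
| Pre ≥140 | 44.4 / 19.8 | 0 / 0 | 25.7 / 10.3 | 40.9 / 18.8 |
| Post ≥160 | 6.3 / 1.3 | 0.36 / 0.11 | 2.51 / 0.55 | 3.72 / 0.89 |

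Across e = 5 to 15, post-infusion readings ≥160 on ramucirumab run from 3.0% to 11.8% over all visits, against 0.2% to 6.5% over dosed visits. Symptoms and diastolic pressure were not modelled.

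**Layout alone**

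Suppose 30% of patients reach the top category once, spread evenly over six visits. Each visit then shows 0.30/6 = 5%; with 20% it is 0.20/6 = 3.3%. These are assumed rates. The effect comes from the by-visit layout and would appear with no infusion withheld.

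**The case against.** The strongest reply is that the SAP excludes nothing. A reader might infer that the table discards the readings that show ramucirumab's hypertension. The text does not say so. The reading that triggers a delay may well be the scheduled pre-infusion reading, and the SAP is silent on where it goes. If withheld-visit readings are included, the selection described above does not arise. This stands: the defect is an unstated rule, not a stated exclusion.

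A reader might also infer that the top category is empty by construction. The documents do not support that either. Exclusion criterion 30 says "CTCAE Version 4.0 defines uncontrolled hypertension as Grade >2 hypertension" and describes it clinically as "the patient continues to experience elevated blood pressure (systolic >160 mm Hg and/or diastolic >100 mm Hg"), but the sentence goes on to require that this is despite medication. It does not make any single reading of 160 or more a Grade 3 event. Table JVDE.3 acts on grade, not on a mmHg cut, and asymptomatic Grade 2 may be dosed. The zeros in the pre-infusion ≥160 row follow from assuming h = 1. Post-infusion readings also stay in the table and can be high.

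Third, a reader might infer that the trial would miss the hypertension signal. It would not. SAP 6.5.6.3 reports treatment-emergent events by maximum grade, which is a per-patient worst-grade count. SAP 6.5.6.4 covers events of special interest and events leading to dose modification or discontinuation, and SAP 6.5.6.1 gives reasons for dose adjustments. Vital signs are listed. None of these requires that an infusion was given.

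What remains is narrower. The event outputs rest on what investigators report; Protocol 10.3.1 asks for vital-sign findings that lead to a diagnosis. A listing gives no comparison between arms. The measured values are the check on event reporting, and their only summary has an unspecified rule where it matters most. Day 30 is weak support, being about 30 days after the decision to stop treatment.

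**Conclusion.** The concern holds in limited form. The blood-pressure table in SAP 6.5.6.5 may understate high readings, because the handling of readings at withheld infusions, unscheduled visits and Day 30 is not stated. Any loss would be greater in the arm with more hypertension. Independently of that, the layout never gives the number of patients who ever reached a category.

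The size cannot be taken from the documents. On the assumed +10 mmHg, the between-arm difference in pre-infusion readings ≥160 lies anywhere from 4.8 points (nothing lost) to zero (every such infusion withheld and its reading left out). For pre-infusion readings ≥140 the difference is 44.4 − 19.8 = 24.6 points over all visits. Over dosed visits it is 0, 15.4 or 22.1 points when 0%, 50% or 100% of the 140-<160 visits are dosed.

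This is an inexpensive improvement to a descriptive safety summary. It is not an error that threatens the trial's conclusions.

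**What to change.** In SAP 6.5.6.5:

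1. Add a per-patient shift table from baseline to the worst post-baseline systolic and diastolic category, by arm. Use all recorded readings: scheduled or unscheduled, infusion given or withheld. Include Day 30 or flag it separately. This follows the approach already planned for graded laboratory values in SAP 6.5.6.5.1.
2. Keep the by-time-point table, state that readings at visits where the dose was withheld are included, and say which time point they belong to. A scheduled-day rule is one option, since a missed dose has no cycle number.

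The cost is a short SAP edit and one more safety table to produce and review, from data already collected. Dosing, delay and stopping rules are untouched.
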